Study variables were analyzed by appropriate statistical methods to assess for the differences between eyes treated as an entire group, and as broken down between dexamethasone implant and traditional prednisolone drop groups. Correlations between ease of use, intraocular inflammation, and epithelial healing were assessed using χ^2 , t-test, Pearson, and the Fisher Z-transformation test, evaluating the sample correlation r for significance. For independent samples, the t-test or Mann-Whitney-U test will be used for scaled data based on the outcome of the Kolmogorov-Smirnov test for normality of distribution. Ordinal data was analyzed using the Mann-Whitney-U test and chi-square or Fisher's Exact test for nominal data. P-values less than or equal to 0.05 were considered statistically significant. For non-inferiority or equivalency data, 95% confidence intervals were formulated and compared with equivalency margins. Sample size is small secondary to the incidence of the disease (1:2,000)

For any patient deciding to withdraw from the follow-up, the reasons for the withdrawal were recorded for the subsequent analysis in the interpretation of the results. Reasons behind drop out were investigated and included in study results. The authors only analyzed complete cases, as imputing the missing data using single or multiple imputation methods would be confounded by the small sample size. ITT for ease of use was calculated utilizing extremely conservative estimates of a 70% +/- 10% for drops and 90% for dexamethasone insert, while utilizing a two independent sample study with a continuous endpoint, 1:1 enrollment ratio, alpha/beta of 0.05, and power of 95%. We calculated the minimum number of patients needed to enroll as 12.

In order to account for type I errors over multiple endpoints Bonferroni adjustment method was utilized.

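### The 95% power and 12-patient minimum assume a continuous ease-of-use score, but the text available reports ease of use only as yes/no answers

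*Combined protocol and SAP*

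**What the plan says.** The sample-size text in the Biostatistics section takes ease of use as its endpoint. It uses "extremely conservative estimates of a 70% +/- 10% for drops and 90% for dexamethasone insert" and describes a "two independent sample study with a continuous endpoint, 1:1 enrollment ratio, alpha/beta of 0.05, and power of 95" percent. It concludes: "We calculated the minimum number of patients needed to enroll as 12". It does not say whether the 10% is an SD or a range, whether the test is one- or two-sided, or what spread applies to the insert group. The protocol summary plans 20 patients, and Biostatistics adds: "Sample size is small secondary to the incidence of the disease (1:2,000".

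The results text describes an end-of-study questionnaire with a first, a second and a final question: whether directions were easy to follow, whether drops beyond 10 days were cumbersome, and whether drops were hard to remember. Each result is a yes or a no, and the answers to each question were unanimous. The second question is said to concern the prednisolone group. No scale, score, mean or SD for ease of use appears.

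On methods, Biostatistics says "Ordinal data was analyzed using the Mann-Whitney-U test and chi-square or" Fisher's "Exact test for nominal data". It also says "Correlations between ease of use, intraocular inflammation, and epithelial healing were assessed using" a list that includes chi-square, the t-test and Pearson correlation. On multiplicity: "In order to account for type I errors over multiple endpoints Bonferroni adjustment method was utilized". The number of comparisons is not given.

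**The concern.** This is the only power calculation in the text available, and its endpoint type differs from that of the ease-of-use data reported. A mean score with a small SD needs very few patients. A comparison of two proportions 20 points apart needs many more. The 95% figure cannot be carried from one to the other.

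What is at stake is interpretation. A reader who sees 95% power in the plan and unanimous answers in the results could conclude that a 20-point difference in ease of use had been ruled out.

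**Working it through.** **Inputs.** From Biostatistics: 70% for drops, 90% for the insert (difference 20 points), plus or minus 10% for drops, alpha 0.05, power 95%, 1:1 allocation, minimum 12 (6 per arm). From the protocol summary: 20 patients, so 10 per arm at 1:1.

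**1. Reproducing 12, continuous reading.** Assume the 10% is an SD common to both arms. The assumed effect is then 20/10 = 2 SD. The normal approximation is n per arm = 2 × SD² × (z_alpha + z_beta)² / difference².
- One-sided 0.05: 2 × 100 × (1.645 + 1.645)² / 400 = 5.41, rounded up to 6 per arm, 12 in total.
- Two-sided 0.05: 2 × 100 × (1.960 + 1.645)² / 400 = 6.497 with unrounded z values. That is 6 per arm if rounded to nearest and 7 (14 in total) if rounded up.
- Two-sided with an insert SD of 9 (a further assumption): (100 + 81) × (1.960 + 1.645)² / 400 = 5.88, rounded up to 6 per arm.

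So 12 is roughly reproduced, and more than one route leads to it.

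**2. The same reading by t-test.** The normal approximation is optimistic at this size. Power for a 2 SD difference at 0.05, before Bonferroni:

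| Per arm | Two-sided | One-sided |
|---|---|---|
| 6 | 87.6% | 94.2% |
| 7 | 92.9% | 97.0% |
| 8 | 96.0% | 98.4% |
| 10 | 98.8% | 99.6% |

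Two-sided 95% needs 8 per arm. The planned 10 per arm exceeds that.

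**3. Proportion reading.** Assume instead that 70% and 90% are response proportions, with two-sided 0.05. For 95% power, n per arm = [1.960 × √(2 × 0.8 × 0.2) + 1.645 × √(0.7 × 0.3 + 0.9 × 0.1)]² / 0.2² = (1.109 + 0.901)² / 0.04, which is about 101. Power by exact enumeration, before Bonferroni:

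| Per arm | Fisher | Uncorrected chi-square |
|---|---|---|
| 6 | 0.6% | 14.2% |
| 10 | 5.7% | 14.3% |

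If the 10% is a range for the drops rate (80% to 60%), 10 per arm gives 1.2% to 15.2% (Fisher) or 4.6% to 29.1% (chi-square), and 95% power needs 329 to 52 per arm. No two-proportion calculation comes near 12: at 70% vs 90% and 95% power, the smallest total is 168 (one-sided, 84 per arm).

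**4. What the unanimous answers allow.** Take one item asked of both groups and assume 10 of 10 in each gave the same answer. The Wilson limit for 10/10 lies 3.84 / (10 + 3.84) = 0.278 from 1, so the Newcombe 95% interval for the difference is about ±28 points. Other standard methods give ±22 (Agresti-Caffo) to ±29 (Miettinen-Nurminen). Unanimity does count against true rates of 70% and 90%: 0.7¹⁰ × 0.9¹⁰ = 0.0098, about 1.0%. It remains compatible with 80% and 100%: 0.8¹⁰ × 1 = 0.107, or 10.7%. A 20-point difference is therefore not excluded.

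**The case against.** The strongest reply is that the calculation is coherent on its own terms. The text says continuous, a percentage score is a natural reading of a mean with a plus-or-minus, and naming the t-test and Pearson correlation for ease of use suggests a numeric measure. On that reading the planned 20 patients give more than the stated power. Part of the document between the Biostatistics text and the results was not available and could define a scale. All of this stands. It limits the conclusion to ease of use as reported in the text available; it does not show that no score was collected.

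It is also fair that little follows in practice. The questionnaire results carry no test, p-value, interval or equivalence claim, 20 patients were planned rather than 12, and the plan already calls the sample small. That keeps the point minor.

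Three stronger readings are tempting, and the documents do not support them.
- A reader might infer that 12 betrays an undisclosed one-sided test. It does not: the two-sided figure of 6.497 rounds to 6, and a slightly smaller insert SD also gives 6.
- A reader might infer that the study was really sized on proportions and had only 6% or 14% power. The text says continuous, and no proportion calculation yields 12. Those powers show how far the claim fails to transfer to yes/no data; they do not correct an arithmetic slip.
- A reader might use those low powers to interpret the unanimous answers. Power computed beside results already in hand adds nothing to the interval.

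**Conclusion.** The point holds in limited form and is minor. The 95% power and 12-patient minimum rest on a continuous score that the text available neither defines nor reports, so they do not describe the three yes/no items.

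The size depends on the reading. With a common SD of 10 (assumption), two-sided t-test power is 87.6% for 12 patients and 98.8% for 20. With 70% and 90% as proportions (assumption), 20 patients give about 6% (Fisher) or 14% (chi-square). All figures precede a Bonferroni adjustment whose number of comparisons is not stated. The ±28-point interval assumes 10 of 10 answering in each group. The questionnaire results do not give the numbers answering, and analysis was of complete cases. No between-group interval exists for item 2. Describing the assumptions as extremely conservative is hard to reconcile with a 2 SD effect, but that depends on the same SD assumption and is secondary.

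**What to change.** Wording only, in one of two forms.

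- **If a scaled ease-of-use score was collected:** define and report it, state the SD and sidedness used, and restate the power for 12 and for 20 patients by t-test.
- **If not:** state that the 95%/12-patient calculation assumed a continuous score and does not apply to the yes/no items. Withdraw it, and the description of its inputs as extremely conservative, as support for those items. Give the sample-size rationale as feasibility, based on disease incidence. For items 1 and 3 only, report the 95% interval for the between-group difference from the actual numbers answering, and say that a 20-point difference is not excluded if the interval is as wide as calculated here. Give no between-group interval for item 2, and do not use power figures to interpret the observed answers.

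No patients or new data are needed. The cost is a less favourable statement of power.

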11/20/2023

[figure not shown]
Dear FDA Clinical Trials Review Board,

Please find attached the *study protocol and statistical analysis plan* document as requested on the PRS System.

This is for the study: *Intracanalicular Dexamethasone Insert for Post-Corneal Cross-Linking Inflammation and Pain- The LINK Study* (IND 146603; NCT04168112)

Please do not hesitate to contact me with any questions or concerns regarding this document.
Thank you for your time and consideration.

Sincerely,

[name], DO
SightMD
[name]
[name]
[contact]

*Intracanalicular Dexamethasone Insert for Post-Corneal Cross-Linking Inflammation and Pain-
The LINK Study*

Protocol in brief: This prospective, open-label, single-center, randomized, investigator-sponsored clinical study sought to investigate the efficacy of dexamethasone intracanalicular insert on post-corneal crosslinking inflammation and pain in keratoconus patients. This study planned to enroll 20 patients and follow patients over the course of several study visits [(postoperative day (POD) 1, POD-3, POD4-7, POW2, POW3 and POW4]. It is anticipated that corneal re-epithelialization will occur within the first postoperative week, but patients were be followed closely for documentation of therapeutic effect for 30 days due to duration of steroid therapy (i.e. dexamethasone intracanalicular insert or use of Prednisolone acetate 1% ophthalmic solution tapered over 1 month in the following schedule: 4 times daily x1 week, 3 times daily x 1 week, 2 times daily x 1 week, and daily x 1 week). All patients will receive postoperative fluoroquinolone antibiotic eye drops with instructions for use (i.e. 1 drop in operative eye 4 times daily x 10 days). All patients were evaluated for pain scores, rate of corneal re-epithelialization, ease of use of the post-crosslinking regimen, and need for rescue pain medication after standard bilateral epithelium-off crosslinking.

Biostatistics

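### The sample size uses an unadjusted alpha of 0.05 while the same section declares Bonferroni, so 95% power at 12 patients does not match the stated multiplicity rule; the planned 20 largely cover the gap

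*Combined protocol and SAP*

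**What the plan says.** The sample-size statement in the Biostatistics section concerns ease of use alone. It assumes "70% +/- 10% for drops and 90% for dexamethasone insert", treats the comparison as a "two independent sample study with a continuous endpoint" with a "1:1 enrollment ratio", and sets "alpha/beta of 0.05, and power of 95" per cent. It concludes: "We calculated the minimum number of patients needed to enroll as 12".

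The paragraph after it reads: "In order to account for type I errors over multiple endpoints Bonferroni adjustment method was utilized". Earlier in the same section, the significance rule is p at or below 0.05, with no mention of adjustment.

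The Protocol in brief adds two relevant facts. Enrolment was set above the calculated minimum: "This study planned to enroll 20 patients". Four outcomes are named: "All patients were evaluated for pain scores, rate of corneal re-epithelialization, ease of use of the post-crosslinking regimen, and need for rescue pain medication". The text available gives no count of endpoints for the Bonferroni family, no adjusted alpha, and no statement on whether ease of use belongs to the family.

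**The concern.** A power figure belongs to one test at one threshold. If ease of use is one of m endpoints under Bonferroni, it is tested at 0.05/m, and power calculated at 0.05 is not the power of that test. Three statements in one section (sizing at 0.05, significance at p ≤ 0.05, Bonferroni over several endpoints) cannot all describe the same decision rule unless ease of use stands outside the family or the p-values are reported after adjustment. The text available says neither.

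At stake is whether a reader can rely on the stated 95%. The mismatch is also separate from the choice of endpoint: if the ease-of-use measure were redefined and re-sized at 0.05, the same gap would remain.

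**Working it through.** **Inputs.** From the sample-size statement: difference 90 − 70 = 20 points, 1:1 allocation, alpha 0.05, power 95%, minimum 12 patients (6 per arm). From the Protocol in brief: 20 patients planned (10 per arm at 1:1). Assumptions: the ±10% is an SD common to both arms, so d = 20/10 = 2; the test is two-sided, since sidedness is not stated; ease of use is in the Bonferroni family; all enrolled patients are analysed.

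**Step 1: reproduce the 12.** By normal approximation, n per arm = 2(z₁₋α/₂ + z₀.₉₅)²/d².
- Two-sided: 2 × (1.960 + 1.645)²/4 = 6.50 per arm. This is 14 in total rounded up, or 12 rounded to nearest.
- One-sided: 2 × (1.645 + 1.645)²/4 = 5.41, so 6 per arm and 12 in total.
- The two-sided t-test needs 8 per arm, 16 in total.

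The 12 is therefore consistent with a normal-approximation calculation at the stated, unadjusted 0.05.

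**Step 2: power at 12 before any adjustment.** The noncentrality is d√(n/2) = 2√3 = 3.464.
- Normal approximation: Φ(3.464 − 1.960) = Φ(1.504) = 93.4%.
- Noncentral t, 10 degrees of freedom, critical value 2.228: 87.6%.

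**Step 3: power at alpha = 0.05/m.** The number of endpoints m is an assumption, so a range is shown. At 20 patients the noncentrality is 2√5 = 4.472, with 18 degrees of freedom for the t-test.

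| m | alpha | 12 patients, t / z | 20 patients, t / z | total N for 95%, t / z |
|---|---|---|---|---|
| 1 | 0.05 | 87.6% / 93.4% | 98.8% / 99.4% | 16 / 14 |
| 2 | 0.025 | 78.1% / 88.9% | 97.2% / 98.7% | 18 / 16 |
| 3 | 0.0167 | 71.4% / 85.8% | 95.6% / 98.1% | 20 / 18 |
| 4 | 0.0125 | 66.3% / 83.3% | 94.2% / 97.6% | 22 / 18 |
| 6 | 0.0083 | 58.9% / 79.6% | 91.8% / 96.7% | 24 / 20 |
| 10 | 0.005 | 49.5% / 74.4% | 87.8% / 95.2% | 26 / 20 |

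**Step 4: separate the causes at m = 4 and 12 patients.** Bonferroni accounts for 87.6 − 66.3 = 21.3 points by t-test, or 93.4 − 83.3 = 10.1 points by normal approximation. The rest of the distance from 95% (7.4 points by t, 1.6 by z) is already there at 0.05 and comes from the two-sided test, the rounding and, for the t figure, the exact method.

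**Step 5: sidedness.** A one-sided test at 0.05/m has the critical value of a two-sided test at 0.10/m. A one-sided family of two thus matches the m = 1 row and a one-sided family of four matches the m = 2 row. Power at 12 patients is still below 95% in both.

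**The case against.** The strongest reply is that 12 is a floor and the trial planned 20. On the plan's own effect size and SD, 20 patients give more than 95% by either method for two or three endpoints. With four, the t-test falls short by 0.8 points and the normal approximation does not fall short at all. This stands. A reader might infer from the 66.3% figure that the planned trial is badly underpowered, and the documents do not support that. What remains is that the plan attaches its 95% to 12, states no power at 20, and analyses complete cases only, so dropout would bring the analysed number closer to 12.

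A second reply is that an adjusted threshold may never have been applied to ease of use. The family is undefined in the text available, part of the document was not available and may list it, and the four outcomes in the Protocol in brief are not called a family. The results text also calls a pain comparison with p = 0.036 significant; taken as a raw p-value, it fails any Bonferroni threshold for two or more tests (0.025 or lower). This stands too: it cannot be asserted that the test performed used 0.0125. But it does not remove the mismatch. Either the sizing ignores the declared adjustment, or the declared adjustment does not govern the significance rule, or ease of use lies outside it. The plan should say which.

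A third reply is that little follows in practice. Ease of use is reported as yes/no answers, with every patient giving the same answer to each question, and no continuous comparison is shown. That limits the consequence for the reported conclusions but leaves the stated figure uncorrected.

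**Conclusion.** The point holds as a mismatch between the alpha used for sizing and the declared multiplicity rule. If ease of use is in the Bonferroni family, 95% is not the power at 12 patients for any family of two or more: 78.1% (t) or 88.9% (z) with two endpoints, 66.3% or 83.3% with four, 49.5% or 74.4% with ten. At the planned 20 the loss is slight or absent for small families. It reaches about 7 points (95 − 87.8) only by t-test with ten endpoints; the normal approximation still gives 95.2% there.

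Two further inferences should be resisted. The whole fall from 95% to 66.3% is not due to Bonferroni; about 21 points by t-test, or 10 by normal approximation, are. And placing ease of use outside the family at 0.05 would not by itself make the 12-patient statement true, because the two-sided t-test then gives 87.6%.

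All figures rest on d = 2 with ±10% read as a common SD, a two-sided test and equal arms. The adjusted figures also assume that ease of use is in the family and that its size is as shown.

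**What to change.** State which endpoints form the Bonferroni family and the resulting alpha, and reconcile both with the p ≤ 0.05 rule, including whether reported p-values are raw or adjusted. Replace the claim of 95% power at 12 patients with the power of the planned 20 at that alpha, naming the test and sidedness. If the four outcomes in the Protocol in brief are the family, this is about 94% by two-sided t-test.

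Alternatively, if it was pre-specified, state that ease of use is the single endpoint tested at 0.05 outside the Bonferroni family. The figures still need restating: by two-sided t-test, 12 patients give 87.6%, 16 give 96.0% and the planned 20 give 98.8%.

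Either route costs a few sentences and one recalculation. Neither needs added enrolment.

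### The stated minimum of 12 patients reaches 95% power only on unstated assumptions; a two-sided t-test with SD 10 in both arms has 87.6% at 12 and needs 16

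*Combined protocol and SAP*

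**What the plan says.** The sample-size statement is in the Biostatistics section. It takes ease of use as the endpoint, with values of "70% +/- 10% for drops and 90% for dexamethasone insert", "utilizing a two independent sample study with a continuous endpoint", a 1:1 ratio, "alpha/beta of 0.05" and 95% power. It ends: "We calculated the minimum number of patients needed to enroll as 12".

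On analysis, the same section says: "For independent samples, the t-test or Mann-Whitney-U test will be used for scaled data", the choice depending on a normality test. On the threshold it says: "P-values less than or equal to 0.05 were considered statistically significant". It also reports a Bonferroni adjustment across multiple endpoints, without saying how many endpoints or whether ease of use is among them, and it restricts the analysis to complete cases. The opening protocol summary gives planned enrolment as 20.

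Three inputs are missing: whether the calculation is one- or two-sided, whether it uses a normal or a t formula, and the SD in the insert arm. The +/- 10% is not labelled as an SD.

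**The concern.** A printed minimum tells the reader how small the analysed sample can be while the stated power still holds. Here that is relevant because only complete cases are analysed. With 20 planned, a minimum of 12 suggests that 8 patients could be lost with power still at 95%. If the minimum is 16, that margin is 4 (both counts assume the remaining patients split evenly between arms).

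The figure looks low for the test named. With 6 per arm the t-test has 10 degrees of freedom, and a normal approximation, which treats the SD as known, overstates power noticeably at that size.

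**Working it through.** **Inputs.** From the Biostatistics section: means 70 and 90 (difference 20), alpha 0.05, power 95%, 1:1 allocation, total 12, read as 6 per arm. Assumed: +/- 10 is an SD, and the insert arm has the same SD. The standardised difference is then 20/10 = 2.0.

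**Reproducing 12.** The normal-approximation size per arm is n = 2 × (z_alpha + z_beta)² × (SD/difference)².

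- One-sided: 2 × (1.645 + 1.645)² × 0.25 = 5.41, rounded up to 6 per arm = 12 patients. This matches the printed figure.
- Two-sided: 2 × (1.960 + 1.645)² × 0.25 = 6.50 (6.497 before rounding). A minimum must be rounded up, giving 7 per arm = 14 patients. Only rounding down gives 12.

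**Power at 6 per arm, SD 10 in both arms.** The noncentrality is 2.0/√(2/6) = 3.464. The t-test uses 10 degrees of freedom, with critical value 2.228 two-sided and 1.812 one-sided.

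| Method | Power at 12 patients | Patients for at least 95% |
|---|---|---|
| Normal, one-sided | 96.6% | 12 |
| Normal, two-sided | 93.4% | 14 |
| t-test, one-sided | 94.2% | 14 |
| t-test, two-sided | 87.6% | 16 |

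Two-sided t-test power by size per arm: 6, 87.6%; 7, 92.9%; 8, 96.0%; 10 (the planned 20 patients), 98.8%. For the other named test, a simulation of the two-sided Mann-Whitney U test on normal data gives about 83% at 6 per arm and 98% at 10 per arm.

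**Sensitivity to the insert SD.** Keep SD 10 for drops and vary the insert SD. With equal arms the effective SD is √((10² + SD²)/2). Two-sided t-test, 6 per arm:

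| Insert SD | Effective SD | Power at 12 patients |
|---|---|---|
| 7 | 8.63 | 95.0% |
| 9 | 9.51 | 90.6% |
| 10 | 10.00 | 87.6% |
| 12 | 11.05 | 80.6% |

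On the two-sided normal formula, an insert SD of 9 gives (100 + 81) × (1.960 + 1.645)²/400 = 5.88, so 6 per arm = 12.

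**Sensitivity to Bonferroni.** If the adjustment covers ease of use, with 2 to 6 endpoints (number assumed) and SD 10 in both arms, two-sided t-test power falls to 78.1% to 58.9% at 12 patients and 97.2% to 91.8% at 20.

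**The case against.** The strongest reply is that the plan never commits to a two-sided test, a t formula or equal SDs, and that 12 is exactly what the standard one-sided normal formula returns. A threshold of 0.05 does not settle sidedness, since one-sided p-values can be read against it too. An insert SD a little below 10 also rescues 12 with two-sided testing: SD 9 on the normal formula, SD 7 on the t-test. All of this stands. A reader might infer that 12 cannot be obtained from the plan's inputs, or that it is plainly an arithmetic error. The documents do not support that, because the inputs are incomplete.

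Two-sided testing is nevertheless the better reading. The Biostatistics section speaks of differences between groups and names no direction or one-sided alpha. The results narrative on pain reports significance in favour of prednisolone (p=0.021 and p=0.036), which a test directed only at insert benefit could not produce. Pain is a different endpoint, so this is supporting evidence and not proof. With SD 10 in both arms, the t-test also misses 95% at 12 when one-sided (94.2%).

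A second reply is that the t-test is not the only planned test. That is correct: Mann-Whitney U is the alternative for scaled data, although it does worse at 6 per arm. The ease-of-use items in the results narrative are yes/no answers, which under the plan's own rule would go to chi-square or Fisher's Exact. The figures above therefore describe the continuous endpoint that the sizing assumes, not those items.

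A third reply is that nothing turned on 12, because 20 were planned and the document already reports results. This largely stands. A reader might infer that the study was too small for its sizing endpoint. On the plan's assumptions at unadjusted alpha it was not.

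**Conclusion.** The point holds in a limited form. The 95% claimed for 12 patients depends on choices the plan does not state. With SD 10 in both arms, a two-sided t-test at unadjusted alpha 0.05 gives 87.6% at 12, a shortfall of 7.4 percentage points, and needs 16 patients.

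This rests on four readings: +/- 10% is an SD, the insert arm shares it, 12 is a total, and testing is two-sided. The second matters most. An insert SD between 7 and 12 moves power at 12 from 95.0% to 80.6%.

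The consequence is small. Planned enrolment of 20 gives 98.8% under the same assumptions, and 5 of the 20 would have to be lost before the total fell below 16. What needs correcting is the reported minimum, not the planned enrolment.

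**What to change.** Restate the sample-size sentence with the sidedness, the test or formula, and the SD assumed in each arm. Then choose one:

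- give the minimum as 16 patients (8 per arm) for at least 95% power; or
- keep 12 and give its power as about 88%.

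Both figures are for a two-sided t-test with SD 10 in both arms and unadjusted alpha 0.05. If the sponsor used a different insert SD or a one-sided normal formula, the sentence should say so and give the figure that follows.

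Add that the planned 20 patients give 98.8% at alpha 0.05 on the same assumptions. State whether Bonferroni covers ease of use and over how many endpoints; for 2 to 6 (assumed), the power of 20 patients falls to about 97% to 92%.

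The cost is a sentence or two of text. No extra enrolment is needed, and the only loss is a less favourable stated minimum.

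### Bonferroni is a valid choice, but Holm's step-down procedure over a named family would give the same error control and never less power for the tests

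*Combined protocol and SAP*

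**What the plan says.** The Biostatistics section deals with multiplicity in one sentence, which says that, for type I error, "over multiple endpoints Bonferroni adjustment method was utilized". The text available for this review gives no number of endpoints, no list of family members, no primary endpoint and no adjusted significance level. The text directly after that sentence was not available, so a list could stand there.

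The same section sets a general rule: "P-values less than or equal to 0.05 were considered statistically significant". The sample-size statement uses an undivided alpha: "1:1 enrollment ratio, alpha/beta of 0.05, and power of 95" percent. Protocol in brief states "This study planned to enroll 20 patients" and names four evaluated outcomes: pain, re-epithelialization, ease of use and rescue pain medication. Holm's procedure is not mentioned.

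**The concern.** With m tests in the family, Bonferroni holds every one of them to 0.05/m, whatever happens to the others. Holm orders the p-values and compares them in turn with 0.05/m, 0.05/(m-1), and so on up to 0.05, stopping at the first failure. Neither method needs an assumption about dependence between the outcomes.

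In a trial with about 10 patients per arm and several outcomes, the single-step rule can miss a second or third true effect that Holm would declare at the same family-wise error. The possible loss is power for effects beyond the first. The validity of the error control is not in question.

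**Working it through.** **1. The plan's own sample size.** The inputs, from Biostatistics, are "70% +/- 10% for drops and 90% for dexamethasone insert", read as a difference of 20 with a common SD of 10 (an assumption), with alpha 0.05 and power 95%. The formula is n per arm = 2(z_alpha + z_beta)² × SD²/difference².

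- One-sided: 2 × (1.645 + 1.645)² × 100/400 = 5.4, so 6 per arm and 12 in total. This matches "We calculated the minimum number of patients needed to enroll as 12".
- Two-sided: 2 × (1.960 + 1.645)² × 100/400 = 6.5, so 7 per arm and 14 in total.

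With 10 per arm (20 patients at 1:1), a two-sided t-test at 0.05/4 = 0.0125 still has 94% power for this one outcome, against 99% at 0.05. Bonferroni therefore does not undermine the outcome on which the trial was sized.

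**2. Power for several outcomes.** These are assumptions, because the documents give neither m nor correlations: m = 4, 10 per arm, correlation 0.3, normal outcomes, two-sided t-tests, 20,000 simulated trials per row.

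| Real effects | Average power per real effect, Bonferroni to Holm | All real effects found |
|---|---|---|
| Four at 1.5 SD | 71% to 83% | 35% to 64% |
| Four at 1.0 SD | 33% to 40% | 4% to 15% |
| Two at 1.5 SD, two null | 71% to 74% | 54% to 60% |
| One at 1.5 SD, three null | 71.3% to 71.4% | same |

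The chance of at least one rejection was identical under both methods in every row, because Holm's first threshold is Bonferroni's threshold. No simulated trial had Bonferroni rejecting where Holm did not. Family-wise error stayed below 0.05 for both methods in the rows with null outcomes.

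**3. The printed p-values, taken as unadjusted.** They are 0.021 and 0.036 (pain, POD0 and POD1), 0.061 and 0.152 (re-epithelialization, POD3 and POD1) and 0.518 (baseline IOP). The smallest adjusted value is m × 0.021 under both methods.

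| Family | Smallest adjusted p | Rejections, Bonferroni / Holm |
|---|---|---|
| All five | 5 × 0.021 = 0.105 | 0 / 0 |
| Four, without baseline IOP | 4 × 0.021 = 0.084 | 0 / 0 |
| 0.021, 0.036, 0.061 | 3 × 0.021 = 0.063 | 0 / 0 |
| The two pain tests only | 2 × 0.021 = 0.042 | 1 / 2 |

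The methods differ only in the last row. There, Bonferroni's second adjusted value is 2 × 0.036 = 0.072, and Holm's is max(0.042, 0.036) = 0.042.

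**4. Reliability of those p-values.** The printed POD0 pain summaries are 6.4 ± 1.3 and 6.6 ± 1.62. With 10 per arm (assumed), t = 0.2/√((1.3² + 1.62²)/10) = 0.30 and p is about 0.76. With 20 eyes per arm, treated as independent, p is about 0.67. Neither is near the printed 0.021. For POD1 the same calculation gives 0.097 and 0.018 against the printed 0.036. Step 3 therefore shows how the rules behave and is not evidence about treatment.

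**The case against.** Bonferroni is standard and valid, so choosing it is a matter of preference. This stands: no wrong conclusion follows from the choice.

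The largest gain needs all four outcomes to have large real effects, and the documents do not support that. The printed summaries give standardized differences of about 0.14 for POD0 pain and 0.78 for POD1 pain. Every patient gave the same answers on ease of use. Rescue medication is a yes/no outcome to which the simulated t-tests do not apply. This also stands, and it is why the smaller gains belong beside the larger one.

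Bonferroni has simple matching simultaneous intervals, and the plan compares 95% intervals with equivalence margins. This stands in part. The plan describes ordinary 95% intervals and does not mention simultaneous ones, so the benefit is not visibly used, but it would be lost if they were wanted.

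The document already prints results, so moving now to a more permissive rule is post hoc. This stands and limits what the change can do for the present data.

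A reader might also infer that the more serious fault is that Bonferroni was never applied, since 0.021 and 0.036 are both called significant. If both are unadjusted, 0.036 fails for any m of 2 or more and 0.021 for any m of 3 or more. The document does not say whether they are adjusted, so this cannot be settled from the text. It is a reason to report adjusted p-values under either method.

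**Conclusion.** The point holds as a modest improvement. For the tests, Holm gives the same strong family-wise control as Bonferroni and is never less powerful. Under the stated assumptions (four outcomes, 10 per arm, correlation 0.3, effects of 1.5 SD), the gain in average power is about 11 percentage points if all four effects are real, about 3 if two are, and practically nil if one is. The true gain cannot be stated, because the available text defines neither m nor the family.

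Two stronger readings are not supported. The first is that the trial gives power away for nothing: Bonferroni keeps simple simultaneous intervals, the chance of a first rejection is the same, and the sizing outcome keeps 94% power at m = 4. The second is that Holm would secure the POD1 pain result. That requires a family of exactly the two pain tests, which the available text never defines, and p-values that the printed means and SDs do not reproduce at POD0.

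**What to change.** In Biostatistics, replace the Bonferroni wording with: Holm step-down adjustment at a family-wise two-sided 0.05 over the following outcomes. Then list the outcomes. The four in Protocol in brief (pain, re-epithelialization, ease of use, rescue pain medication) are one possible family. State the visit used for each, or count every tested visit in m. Holm works on p-values from any valid test, so the plan's t, Mann-Whitney and Fisher tests can stay.

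For that family, report adjusted p-values in place of the flat 0.05 rule. Label any re-analysis of the existing data post hoc. Before any adjustment, check the printed pain p-values against the source data.

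The wording change is a sentence plus a list, with no loss of family-wise error control. Any simultaneous intervals would stay Bonferroni-based and may occasionally disagree with the Holm tests, and the plan should say so.
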